### Work package 4: Knowledge exchange, dissemination, impact

# Objective

To share and interpret findings with stakeholders.

### Approach

Knowledge Exchange will involve an interpretive workshop (see WP2), and an online engagement event for a larger audience. Our policy and practice links include charities (Shelter, Crisis, Safer Renting), national government, local government, the London Public Health and Housing Network, Equal England and NIHR ARCs. The research team have an excellent track record in producing material for non-academic audiences as part of an impact pathway and we will consult with practice and public partners on how best to disseminate findings to target audience. We include some relevant letters of support. We have costed for four open access academic publications (noting that not all publications involve project-level fees) and UK conference presentations. For the study to have impact it should inform future decisions to implement SL schemes and influencing national policy on licensing.

# 19. Handling of missing data

Missing data does not constitute a significant issue with the listed data sources and the analyses will be conducted as complete case only.

# 20. Handling of withdrawals and replacements

Not applicable.

# 21. Outcome

Primary and secondary outcomes are described in detail in Section 18 as part of the detailed analysis plan. They are summarised here.

# Work package 1.

#### Area level:

Primary outcome: Mental health and wellbeing (SAMHI)

Secondary outcomes: Emergency hospital admissions: all cause; cardiovascular; respiratory; injuries due to falls or burns; asthma. Reported anti-social behaviour. Population turnover. Average cost of rent.

#### Individual level:

Primary outcome: Self-reported anxiety (ONS APS).

Secondary outcomes: General self-reported health, residential stability (ONS APS).

# Work package 2.

Qualitative 'outcomes': stakeholder acceptability; pathways to impact; unintended and systemic consequences; barriers/facilitators; equity assessment.

### Work package 3.

Outcome: Benefit-cost ratio for SL - to monetise the benefits of SL, we will apply the subjective wellbeing approach described in section 18 to the ONS APS outcome: self-reported life satisfaction.

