# Intervention

This research protocol focuses on one type of regulatory intervention that local authorities have discretion to implement or not implement. The Housing Act 2004, and subsequent revisions in 2015, gave local authorities discretionary powers to implement **selective licensing (SL)** schemes [5]. SL requires landlords in geographically defined areas to pay for a 5-year licence. Fees vary but are around £600 [9,10]. The fees help finance the local authority's regulation of PRS in that area (e.g. housing inspections) although they may not cover the full costs to local authorities. When local authorities inspect PRS homes and find them to be substandard, landlords are expected to pay for the improvements necessary to meet the legal standards.

SL applies to privately rented properties occupied by a single household. Nine out of ten PRS homes meet this description. Houses that include multiple households (Houses in Multiple Occupation or HMOs) are not covered by SL. HMOs have separate license schemes not covered by this study.

Local authorities must obtain approval from national government if a proposed SL scheme covers >20% of their geographical area or affects >20% of privately rented homes in the local authority area. In this study, we will call these 'larger' SL schemes. SL schemes covering up to 20% can be implemented by local authorities without applying for this national government approval. We will call these 'smaller' SL schemes. The smaller schemes therefore have a simpler approval mechanism and they occur most frequently as zoned sub-areas within local authority boundaries.

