The four case study sites have been selected to represent different types of SL (smaller and larger) in different regional contexts (north and south). We will use extrapolation methods that use these two broad characteristics as well as cost information obtained through FOI requests to assign costs to the other local authorities that have implemented SL. We will subtract income from license fees, fines and civil penalties to obtain net costs.

In addition, we will estimate the potential costs saved by the NHS through SL's impact on antidepressant prescribing, mental-health related hospital admissions and all-cause hospital admissions over our sample period. If possible, we will also estimate potential cost savings through impacts on mental health-related benefits. If we find substantial cost savings, we will subtract these from the cost of SL to local authorities to obtain net costs from a public sector perspective.

To estimate net costs from a societal perspective we will add back in any income local authorities generate from license fees, fines and civil penalties and try to estimate the costs landlords incur to remove hazards following the receipt of an improvement notice issued by the local authority following an SL inspection.

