### **Approach**

The economic evaluation will produce a cost-benefit analysis that uses the subjective wellbeing approach to monetise the benefits of SL. A cost-benefit analysis is better suited to assessing the

value of SL than a cost-effectiveness analysis. A cost-effectiveness analysis requires a comparison between alternatives, such as providing patients with a certain disease with usual treatment versus a new treatment. SL has no obvious alternative. Rather than informing policy makers about which of two options to choose to achieve an outcome that has already been agreed is worth achieving, the purpose of this economic evaluation is to inform policy makers whether this type of intervention is worth doing or if local governments' resources might be better spent on different programmes.

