Using the subjective wellbeing approach to determine the monetary value of the benefits of SL avoids the problems of traditional preference-based methods of valuing non-market goods. The subjective wellbeing approach measures people's experiences instead of their preferences. It assesses the impact of non-market goods, policies, or events on how people think and feel about their lives as a whole. This impact is then converted into a monetary figure by comparing it to the effect of income on subjective wellbeing [62]. For example, if a policy increases subjective wellbeing by 0.5 on the 0 to 10 scale and similarly a £5,000 increase in income results in a 0.5 increase in subjective wellbeing, the value of the policy to the individual is assumed to be £5,000. The data on subjective wellbeing is being collected without any reference to the policy under consideration. Thus, the subjective wellbeing approach avoids the two main problems of stated preference methods which attempt to elicit individuals' "willingness to pay" for a particular outcome: When asking people how much they would be hypothetically willing to pay for a certain outcome, they tend to overstate their valuation of a good or they strategically misrepresent their true preferences [62]. The subjective wellbeing approach also avoids the problems of revealed-preference methods, which infer the implicit price of, for example, an environmental amenity by comparing the prices of houses that have similar characteristics except for the level of the environmental amenity. This method requires assuming that housing markets are in equilibrium, that individuals have full information on all house prices and characteristics and that there are zero transaction and moving costs. These assumptions are unlikely to be met [62].

If we measured the benefits of SL only in terms of QALYs or increases in employment rates or reductions in antidepressant prescribing costs to the NHS, we would miss the value of impacts that are difficult to measure but are potentially more important to people. Focusing on outcomes such as QALYs or employment captures the instrumental value but ignores the intrinsic value of improvements in housing quality.

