WP3 Cost-benefit analysis using subjective wellbeing approach

The economic evaluation will produce a cost-benefit analysis that uses the subjective wellbeing approach to monetise the benefits of SL. The starting point for the calculation of the benefits of SL will be the estimate of the impact of SL on the life satisfaction variable from the APS, one of our individual-level outcome measures. We will then follow the procedure described in Dolan et al. (2019) [11]. Essentially, we will use an estimate of the impact of income on life satisfaction from previous research to determine the income change that would be required to achieve the same change in life satisfaction as achieved by SL. Multiplying this income change amount by the number of individuals affected by SL will provide the total benefit of SL from a societal perspectives. All our calculations will be retrospective and estimate the benefits of SL over our 2012 to 2019 sample period. Depending on the results of our analysis of spillover effects, we will adjust the benefit estimate accordingly.

We will calculate the costs of SL from a public sector perspective and attempt to estimate the costs of SL from a societal perspective. To determine the total cost of SL from a public sector perspective over the 2012 to 2019 sample period, we will measure the direct and indirect cost of SL in four case study sites. Accounting data provided by the case study sites will be the starting point for the cost calculation. However, the economic concept of opportunity cost goes beyond accounting cost. For example, local authorities might employ staff specifically for the administration of the SL schemes in their area, so these costs would be included in the accounting data as staff salaries and on-costs. However, staff not specifically employed for SL purposes might also be involved in administering local schemes. Any staff involved in SL will require office space and might need to be trained and supervised. Local authorities need to disseminate information about their SL schemes using their website or other means and maintain the online application system. All these activities incur costs, either directly in the form of money being handed over in payment or indirectly in the form of resources such as staff time or office space not being available for alternative uses.

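### The WP3 benefit-cost ratio is built from point estimates, with no interval, no treatment of a null effect, and a public-sector cost that may be close to zero

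*Protocol*

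**What the plan says.** Protocol section 21 lists one WP3 outcome, "Outcome: Benefit-cost ratio for SL", based on self-reported life satisfaction in the APS. The method is in Protocol sections 9a and 18 and in SAP section 9a. The estimated effect of licensing on life satisfaction is turned into an equivalent income change, using a coefficient from previous research. Then "Multiplying this income change amount by the number of individuals affected by SL will provide the total benefit of SL".

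Costs are measured in four case-study sites and extended to the other authorities by scheme type and region, together with cost information from FOI requests. For the public-sector view, "We will subtract income from license fees, fines and civil penalties to obtain net costs". Substantial NHS savings would also be taken off. Protocol 9a and SAP 9a add an attempt at a societal view, which puts fees, fines and penalties back and tries to include landlords' hazard-removal costs.

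On use, Protocol section 18 says that "the purpose of this economic evaluation is to inform policy makers whether this type of intervention is worth doing". No WP3 passage in either document gives an interval, a way to propagate uncertainty, a sensitivity analysis, a break-even value, or what will be said if the effect is null or negative.

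**The concern.** The ratio combines three uncertain quantities: a survey-based treatment effect, an income coefficient taken from other work, and costs extended from a few sites. A point ratio shows none of that uncertainty. Followed as written, WP3 could report a ratio well above 1 from an effect smaller than its own standard error.

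The denominator is a second weakness. Protocol section 7a says fees help finance regulation but may not cover the full cost. Net public-sector cost could therefore be small, and if fees, fines, penalties and any NHS savings exceed gross cost it is negative. As net cost shrinks, the ratio and its error grow without limit. Once net cost passes zero, the ratio changes sign although the policy has become cheaper.

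At stake is WP3's objective of saying whether licensing is value for money. No WP1 estimate is affected.

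**Working it through.** **Inputs from the documents**
- Income value: in the protocol's illustration a policy raises wellbeing by 0.5 points and "similarly a £5,000 increase in income results in a 0.5 increase in subjective wellbeing". That is £5,000 / 0.5 = £10,000 per point. It is an example, not the coefficient WP3 will use.
- Cost guide: "Fees vary but are around £600" and "SL requires landlords in geographically defined areas to pay for a 5-year licence" (Protocol 7a), so £600 / 5 = £120 per home per year.
- Sample: about 1,000 treated APS respondents a year, about 8,000 over 2012-2019, and three controls per treated (section 11).

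**Assumptions (not in the documents)**
- 2 to 3 people per home; life-satisfaction SD 1.5 to 2.5 points; no clustering.

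**The plan's only precision figure.** Table 1 gives power 0.797 at 0.10 SD for N = 8,000. With SE = √[2(1/n_treated + 1/n_control)]:
- N as total units (2,000 and 6,000): SE 0.0365, power Φ(0.10/0.0365 − 1.96) = 0.782, close to 0.797.
- N as treated units, as labelled: SE 0.0183, power above 0.999, which does not match. It would also need 8,000 treated respondents in each period, whereas 8,000 is the total for all eight years.
- The stated 0.797 implies SE = 0.10 / (1.96 + 0.831) = 0.036 SD, inside the range used below.

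**Standard error of the effect**
- By start year, Table S1 gives 168, 10, 128, 757, 77, 72, 381 and 42 LSOAs for 2012 to 2019 (total 1,635). LSOA-years from the start year on: 7,295 of 13,080 = 55.8%.
- Applied to 8,000 respondents: 4,462 post and 3,538 pre. SE = √[(1/4,462 + 1/3,538) × 4/3] = 0.026 SD.
- One base year of 1,000, with the post period counted only after the start year (5,660 LSOA-years, 3,462 respondents): SE = √[(1/1,000 + 1/3,462) × 4/3] = 0.0415 SD.
- In points: 0.026 × 1.5 = 0.039 to 0.0415 × 2.5 = 0.104.

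**Break-even and spread.** Cost per person-year is £120/3 = £40 to £120/2 = £60. Break-even = cost / £10,000. The ratio is effect / break-even, so its 95% half-width is 1.96 × SE / break-even. This carries the error of the effect only.

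| | Cost = fee | Cost = 10 × fee |
|---|---|---|
| Break-even (points) | 0.004 to 0.006 | 0.04 to 0.06 |
| Break-even / SE | 0.04 to 0.15 | 0.39 to 1.54 |
| 95% half-width of ratio | 13 to 51 | 1.3 to 5 |
| P(ratio > 1), true effect 0 | 0.439 to 0.485 | 0.06 to 0.35 |
| P(ratio > 1), true effect 0.05 SD | 0.87 to 0.97 | 0.60 to 0.91 |

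The probabilities are 1 − Φ(break-even/SE) and Φ[(0.05 × SD − break-even)/SE].

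**Example.** An estimate of 0.03 points is below the smallest SE (0.039). It is worth £300 per person-year and gives a ratio of 300/60 = 5 to 300/40 = 7.5 at fee-level cost.

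**In pounds.** The half-width of benefit per person-year is 1.96 × SE × £10,000, about £764 to £2,034, against a cost of £40 to £60.

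**The case against.** Several points on the other side stand.

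- **The scale is conditional.** The £10,000 comes from an illustration, and occupancy and the SD are assumed. The fee matches neither cost perspective: the public-sector view subtracts it, and the societal view adds landlord costs. The figures are a range under stated assumptions, not a forecast.
- **A reader might infer that the verdict is close to a coin toss.** The documents do not support that. With break-even near zero, any unbiased estimate falls above it about half the time when the true effect is zero, however precise it is. With a true effect of 0.05 SD and fee-level cost, the ratio lands above 1 with probability 0.87 to 0.97.
- **A reader might infer that break-even is always a small fraction of a standard error.** It is at fee-level cost. At ten times the fee it is 0.39 to 1.54 standard errors.
- **WP3 is not strictly one ratio.** Section 21 is a summary; Protocol 9a and SAP 9a describe two cost perspectives and a spillover adjustment.
- **Some uncertainty may appear elsewhere.** Life satisfaction is a WP1 secondary outcome with FDR-adjusted tests, so its own uncertainty should be visible there. WP3 also follows the procedure of a cited study that was not available here. If that includes an interval, the plan does not say so.
- **A pass/fail rule at 95% is a convention.** The stated purpose is to inform policy makers, and expected net benefit is another defensible basis.

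None of this supplies an interval for the WP3 result or removes the problem of a net cost near zero.

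**Conclusion.** The gap is real and should be fixed. WP3's outcome is computed from point estimates, nothing in either document propagates the uncertainty of its three inputs, and the public-sector denominator may make the ratio unstable.

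Under the assumptions listed, the 95% half-width is about 13 to 51 ratio units at fee-level cost and about 1.3 to 5 at ten times that. If the true effect is zero, the chance of a ratio above 1 lies between 44% and 49% at fee-level cost and between 6% and 35% at ten times. At 0.05 SD with fee-level cost the side of 1 is fairly secure, but the size of the ratio remains uninformative. Clustering by scheme or authority, and the errors of the income coefficient and costs, are left out and would add uncertainty.

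The claim that the verdict is mostly chance does not hold in general. Because WP3 is downstream of WP1 and neither primary outcome is touched, this is a should-fix point, not one that undermines the impact evaluation.

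**What to change.** Amend Protocol section 21 and the WP3 text in SAP 9a before the outcome analysis. For each cost perspective (public sector and, if achieved, societal):

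- Make net benefit the main result, with a 95% interval and the break-even life-satisfaction effect. Give the ratio as secondary. Net benefit stays well behaved when net cost is near zero or negative.
- Build the interval from three sources: the estimated sampling distribution of the life-satisfaction effect, using whatever inference WP1 adopts, clustered at scheme or authority level; draws of the income coefficient from its published standard error; and low, central and high cost cases for the extrapolation. Bootstrapping appears in the plan only for the power calculation, so the inference method has to be named.
- State that an interval spanning break-even will be reported as not establishing value for money either way.

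The cost is some SAP wording and a little analysis time. The downside is that the headline may be inconclusive.

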# 22. Data confidentiality statement

Quantitative analyses will only involve de-identified secondary data and be carried out on password-protected university servers unless otherwise specified by agreements with data providers.

Agreements with data providers will be adhered to – including use of secure data environments. The qualitative component of the study will only collect data from consented participants. The data will be anonymised and stored on secure file servers. We will also respect participants' right to withdraw from the study at any point.

# 23. Follow-up

The quantitative part of the study will only involve deidentified data where follow-up is not possible.

The qualitative part of the study mostly consists of single participation points (i.e. a single interview or workshop attendance) for stakeholders who participate. However, we have allowed ourselves some flexibility to re-interview a small number of participants. We have done this so that we can ask for further details if we think it helpful or ask about an emerging issue. Our section above on work package 2 includes the statement: "Providing we have capacity and resource, we may conduct a small number of additional or follow-up interviews to provide further data on the issue(s) we focus on (max. 10 extra participants)." We may also invite some interview participants to one of our workshops or ask a workshop participant if they are willing to be interviewed. The information and consent process will make clear that this possibility of follow-up exists and is something that participants are free to accept or decline. Transcripts for follow-up participants will be treated similarly to other transcripts: they will be anonymised and stored securely.

# 24. Plan of study monitoring

# Role of study sponsor and funder

The sponsor is the organisation assuming overall responsibility for the initiation and management of the study. The funder is funding the study following an application process involving internal and external peer review and revision.

The research team are responsible for the study design, conduct, data analysis and interpretation, manuscript writing, and dissemination of results. The research team report to the funder, including reporting of the protocol and outputs. The views expressed are those of the authors and not necessarily those of the NIHR or the Department of Health and Social Care.

#### Roles and responsibilities of study management committees/groups & individuals

Data Monitoring and Ethics Committee (DMEC)

The DMEC will meet once a year: extra meetings can be called if there is a need. It consists of three independent experts with expertise in the subject area and in qualitative and quantitative data. The researchers will report to the committee on what we have done to ensure our data collection, storage and use is compliant with good practice, and whether or not the primary research is generating any harms or ethical issues. We are using 'routine' secondary data for our impact and economic evaluations: hence we will provide information to the DMEC to show we are meeting our ethics requirements and data agreements relating to the use of those data. Our only primary data collection is qualitative (the WP2 process evaluation). We will share details of our recruitment and consent process, and data privacy and security, and update on any emergent issues during the study. In a worst case scenario, we would call the DMEC to consider how to respond in the event an emergent problem serious enough to require a decision about continuing the study. We cannot predict all potential circumstances that would lead to such a scenario, but we assume it would be something important enough to challenge our view that the study carries no serious risk of harm.

### Independent Steering Committee

The role of the Committee is set out here and repeated below.

The role of the Steering Committee is to provide overall supervision for a project on behalf of the study's Sponsor and Funder and to ensure that it is conducted to the rigorous standards set out in the UK Policy Framework for Health and Social Care and the Guidelines for Good Clinical Practice.

The day-to-day management of the study is the responsibility of the Chief Investigator, and as such the Chief Investigator may wish to set up a separate Study Management Group to assist with this function.

The main features of the Steering Committee are as follows:

- To provide advice, through its Chair, to the study's funder, sponsor, Chief Investigator, host institution, and contractor
- To concentrate on the study's progress, adherence to the protocol, and patient safety (where appropriate), and to consider new information of relevance to the research question
- To uphold the rights, safety and well-being of the participants: these are the most important considerations and should prevail over the interests of the research
- To ensure appropriate ethical and other approvals are obtained in line with the project plan
- To agree proposals for substantial protocol amendments and provide advice to the sponsor and funder regarding approvals of such amendments
- To provide advice to the investigators on all aspects of the study

Constitution of a Steering Committee

The relevant NIHR Programme Director will review the nominees and appoint the Chair and members. Independent members must make up a minimum of 75% of the Committee membership. The minimum quoracy for any Steering Committee meeting to conduct business is 67% (two thirds) of the appointed membership. Only appointed members will be entitled to vote (irrespective of their level of independence) and the Chair will have a casting vote. The Chair and members must sign and maintain a log of potential conflicts and/or interests. Attendance at Steering Committee meetings by non-members is at the discretion of the Chair. The primary Steering Committee reporting line is via the Chair to the relevant NIHR Programme Director; however, communication is likely to be between the Chair and the NIHR Research Manager who has day to day responsibility for the study.

The Committee will include representatives with the following expertise: NIHR PHR project management, qualitative research methods, statistics, economics, public involvement.

The Steering Committee will meet at least once a year and at least three times over the study periodS. Meetings may be online or face to face.

